The aim of the TIME study is to validate the clinical diagnostic performance of previously defined diagnostic thresholds of Pockit diagnostics' algorithm. Results of this study will direct the development of a diagnostic test for identifying LVO patients in the field, directing them to EVT centre, ultimately enabling faster treatment, and improving patient outcomes.

3. Aim of the study

The primary aim of this study is to validate the clinical diagnostic performance of previously defined cut-off points on the plasma concentration of D-dimer and GFAP, combined with stroke severity scales (FAST-ED, FAST, EMSA, RACE, C-STAT).

The secondary aim of the study is to optimise the cut-off points of the diagnostic algorithm for LVO detection, in a larger and inter-racial patient population.

4. Study endpoints

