4.2. Secondary outcomes

Secondary outcomes will be optimised values of ut-off points for the different diagnostic algoirthms (one per stroke severity scale evaluated) obtained in a larger interracial population.

5. Study design and methodology

The TIME study is designed as an observational prospective cohort study.

This study is designed to validate candidate biomarkers according to the STARD principles (http://www.equator-network.org/reporting-guidelines/stard/).

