5.3. Diagnostic criteria

Patients admitted to the ED with suspected stroke will be recruited in the study. Patient population is expected to be composed of ~50% ischemic strokes (of which ~30-40% could have LVOs), ~40% stroke mimics, and ~10% haemorrhagic strokes.

Final diagnosis of stroke subtype or stroke mimics will be established based on CTbased and MRI-based neurologist report. Diagnosis of ischemic stroke will be based on a positive result from MRI scan. Diagnosis of LVOs will be based on results interpretation from CT angiography. Diagnosis of haemorrhagic stroke (ICH or subarachnoid haemorrhage) will be based on positive results from CT scan and, where possible, MRI scan too. Diagnosis of stroke mimics will be based on negative results from both CT scan and MRI scan. Final diagnosis of stroke mimics (i.e. migraine, encephalitis, epilepsy, etc) will be obtained from patient data, where possible. All diagnostic results will require interpretation from a qualified stroke neurologist.

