6.4. Sample size estimation

The proposed intended use of the test is to rule in patients with LVO to redirect them to EVT-capable centers from a population of suspected stroke, thus we powered the study on specificity. Assuming a prevalence of 20%, a minimum specificity of 90%, a two-tailed 5% type I error rate (**a**) and 90% power (**β**), a sample size of 329 suspected stroke patients with 66 LVO cases would detect a diagnostic specificity of 95% (95%CI: 90%–100%) for each

algorithm. Accounting for 20% of data loss due to missing patient data or sample lysis, a final number of 395 patients will be required.

Sample size estimation was performed according to Chu and Cole⁸.

Prevalence of LVO/ischemic stroke will be monitored during recruitment to ensure that calculated sample size is appropriate for actual prevalence. A prevalence in the range of 10-30% LVO will be accepted. In case observed prevalence will be outside the acceptable range, sample size will be re-estimated and recruitment size adjusted accordingly.

7. Data management

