7.4. Data analysis plan

Clinical and biomarker data will be curated after clinical and technical monitoring to assure maximum validity of the data utilised to construct the algorithm. Any subject matching

criteria as defined in section "6.3 – Withdrawal criteria" will not be incorporated into the primary analysis. This data is quarantined for a separate sub-group analysis where relevant.

Data exploration

Data will be explored by generating box plots of blood biomarker concentrations (plasma or whole blood) and clinical data, according to stroke subtypes. Concentrations of blood biomarkers and clinical data (where applicable) may undergo pre-processing and/or transformations to ensure statistical assumptions are met prior to analysis. Akaike information criterion (AIC) will be used to assess the need of transformations.

Whole blood biomarker concentrations

Plasma concentration of individual biomarkers will be adjusted based on whole bloodto-plasma (WBP) ratios, in order to obtain whole blood biomarker concentrations. Values of biomarker concentrations (plasma or whole blood) will be reported with corresponding values of standard error of the mean (s.e.m.).

Covariate analysis

Association between clinical variables and concentration of individual blood biomarkers will be assessed. A linear regression model between biomarker concentration (as the outcome) and key clinical covariates will be generated.

Biomarker kinetics

To assess the effect of biomarker kinetics on diagnostic performance, patient population will be divided into 3-hour and 6-hour bins based on their stroke onset to blood collection time and multivariate logistic regression will be performed on each population bin separately. Alternatively, the distribution of stroke onset to blood collection times will be assessed and the population will be divided into quartiles or halves, and compared. Results from this analysis will be compared to results obtained on the whole population and will inform if the test will be limited to a specific time window from stroke onset.

Diagnostic performance

Values of diagnostic accuracy, sensitivity, specificity, positive and negative likelihood ratios will be calculated and reported with confidence intervals. ROC curve will be drawn and the area under the ROC curve will be reported with confidence intervals. Confidence intervals will be estimated via 2000 bootstrapped replicates.

Biomarker diagnostic thresholds

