Thresholds of individual biomarkers already established by Pockit diagnostics will be validated for their diagnostic performance. If the accuracy achieved by the model is below acceptable levels (specificity <90% and/or sensitivity<60%) we will aim to refine the model using data from our 395 patient cohort.

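### Section 7.4 gives no optimism correction for cut-offs re-optimised, or a model refined, in TIME; if their performance is calculated in the same patients it will generally look too good

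*Combined protocol and SAP*

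**What the plan says.** Section 3 separates two aims. The primary aim is to validate cut-offs on D-dimer and GFAP, defined before the study and combined with a stroke scale. The second is different: "The secondary aim of the study is to optimise the cut-off points of the diagnostic algorithm for LVO detection". Section 4.2 makes the result a secondary outcome: "optimised values of ut-off points for the different diagnostic algoirthms (one per stroke severity scale evaluated"). It lists cut-off values, not performance figures.

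Section 7.4 (Biomarker diagnostic thresholds) tests the established thresholds first. If specificity is below 90% and/or sensitivity below 60%, it continues: "we will aim to refine the model using data from our 395 patient cohort".

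Section 7.4 (Diagnostic performance) lists accuracy, sensitivity, specificity, both likelihood ratios and the area under the ROC curve (AUC). It does not restrict the list to the fixed thresholds. The only resampling in the plan is described there: "Confidence intervals will be estimated via 2000 bootstrapped replicates".

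Two further data-driven choices appear in section 7.4. On transformations: "Akaike information criterion (AIC) will be used to assess the need of transformations". On biomarker kinetics, the results "will inform if the test will be limited to a specific time window from stroke onset".

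**The concern.** A cut-off chosen because it did well in a set of patients has partly been fitted to the chance features of that set. Its sensitivity and specificity in those patients will, on average, exceed what the same cut-off achieves in new patients. A bootstrap that holds the chosen cut-off fixed measures sampling variation around the inflated figure and leaves the inflation in place.

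The fallback matters most, because it applies only when the fixed rule has fallen short. Acceptability is defined there by sensitivity and specificity. Judging whether the refinement worked therefore means calculating those figures, and no other patients are named for the purpose. Section 2 says the results will steer development of a field test, and section 7.5 allows the data to go into product development, validation work and regulatory submissions. Nothing in the plan says how figures for the fixed rule and for a derived rule are to be kept apart in reports.

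**Working it through.** **1. Patient counts.** The plan gives no figure for optimism, so only the counts can be reproduced. An exact binomial test of 95% against 90% specificity, with 90% power at one-sided 5%, needs 263 non-LVO patients, and 263 / 0.80 = 328.75, or 329. (The two-tailed label in section 6.4 is a separate matter.) LVO cases: 329 × 0.20 = 65.8, or 66; 329 − 66 = 263.

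Section 5.3 describes a population "expected to be composed of ~50% ischemic strokes (of which ~30-40% could have LVOs), ~40% stroke mimics, and ~10% haemorrhagic strokes". That implies 0.50 × 0.30 = 15% to 0.50 × 0.40 = 20% LVO, so about 49 to 66 of 329. Section 6.4 adds: "A prevalence in the range of 10-30% LVO will be accepted". At 10% there would be about 33 cases.

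**2. Quantity checked.** Optimism = apparent value of the selected rule in the patients used to select it, minus its true value in new patients.

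**3. Assumptions, none from the documents.**
- Three independent normal components (two biomarkers and a scale), coded so that higher favours LVO, each separated by d standard deviations (SD).
- A patient is positive if all components exceed their cut-offs c₁, c₂, c₃; any component may be dropped.
- 8, 15 or 25 candidate cut-offs per biomarker and a 4- or 6-level scale.
- Cut-offs chosen for maximum sensitivity at apparent specificity of at least 90% or 95%, or by Youden index.
- 1,000 simulated cohorts per setting.
- True sensitivity = Π Φ(d − c_k); true specificity = 1 − Π [1 − Φ(c_k)].

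**4. Optimism in percentage points, 66 LVO / 263 non-LVO.**

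| Procedure | Sensitivity | Specificity |
|---|---|---|
| Joint search, d = 0.8 to 1.3 | 4.8 to 8.6 | 1.1 to 1.9 |
| Joint search, d = 2.0 to 2.4 | 2.5 to 5.4 | 0.5 to 1.2 |
| One cut-off, fixed score, specificity target | at most about 0.4 | at most about 0.4 |
| One cut-off, fixed score, Youden | 2.9 to 4.5 | 0.7 to 1.1 |
| Three-predictor logistic refit | 1.0 to 1.5 (specificity target), 4.0 to 5.7 (Youden) | 0.4 to 1.5 |

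The refit also overstates AUC by 0.4 to 1.1 points. Moving a cut-off on a fixed score leaves AUC unchanged. With fewer LVO cases the joint search overstates sensitivity by 3.2 to 10.7 points at 49 and 4.9 to 13.9 at 33.

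**5. Effect on LR+.** In a second simulation, with separations of 1.0, 0.7 and 1.2 SD and a 95% specificity target, mean apparent sensitivity and specificity were 0.485 and 0.952; the true values were 0.427 and 0.937. LR+ = sensitivity / (1 − specificity):
- apparent: 0.485 / 0.048 = 10.1
- true: 0.427 / 0.063 = 6.8
- ratio: 10.1 / 6.8 = 1.5

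A 1.5-point error in specificity is small in itself, but it is large relative to a false-positive rate near 5%.

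**6. Comparison with the 60%/90% levels.** Take d = 1.3 and the 90% specificity target. With equal cut-offs, the false-positive rate per component is 0.10^(1/3) = 0.464, so c = 0.09. True sensitivity is then Φ(1.3 − 0.09)³ = 0.887³ = 0.698. A rule of this class can therefore reach 60%/90%. The searched rule appeared to do so in nearly all simulated cohorts and truly did so in about 36 to 41%.

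**7. Does a correction work?** The search was repeated in each bootstrap replicate, each replicate's rule was applied to the original cohort, and the mean optimism was subtracted. With the separations of step 5 and the Youden criterion, sensitivity was 0.766 apparent, 0.712 corrected and 0.698 true. The excess fell from 0.766 − 0.698 = 6.8 points to 0.712 − 0.698 = 1.4. In the equal-separation model, at 66 LVO, 1.1 to 2.5 points of sensitivity and 0.2 to 0.6 of specificity remained.

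Intervals need the same care. In that model, nominal 95% percentile intervals with cut-offs held fixed covered true sensitivity in 49 to 85% of cohorts. Shifting them by the mean optimism gave 63 to 96%.

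**The case against.** **The harm is conditional and secondary.** The secondary outcome is a set of cut-off values, the performance measures of section 4.1 belong with the primary aim, and refinement happens only if a trigger is met. This stands. A reader might infer that the main validation is contaminated, or that the plan commits itself to reporting inflated figures. Neither is supported: the primary analysis uses thresholds fixed beforehand, and the plan is silent on performance of a derived rule.

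**Section 7.5 is a general clause on data use.** This also stands. It does not say that a derived rule's figures will be presented as validation. It shows only that nothing prevents such a reading.

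**Specificity, on which the study is powered, is overstated by less than 2 points at 66 LVO, and by almost nothing for one cut-off set to a specificity target.** This is correct under the assumptions used. But sections 3 and 7.4 describe cut-offs on individual biomarkers combined with a scale, which makes a joint search the more natural reading. The likelihood ratios also magnify small errors in specificity.

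**The comparison with 60%/90% depends on the inputs.** It does. With markers at 1.0 SD the picture looks worse, since no cohort's rule truly reaches both levels. That is no evidence of optimism: the best true sensitivity at 90% specificity is then Φ(1 − 0.09)³ = 0.549, so no such rule could succeed. At 1.6 SD the misses come only from specificity falling slightly short.

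**Not every choice can be replayed in a replicate.** This is right for the time window, which section 7.4 leaves to judgement with alternative groupings. The fix allows for it.

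**Conclusion.** The point holds as a gap in the analysis plan for the secondary aim and the refinement fallback. Confidence is high that no correction is stated and that performance calculated in the same patients would be too favourable. Whether harm follows depends on whether such performance is calculated and how it is reported, which the plan does not say.

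The documents give no marker distributions, combination rule or search criterion, so the size cannot be derived from them and no simulated figure is a bound. Under the assumptions above, a joint search at 66 LVO / 263 non-LVO overstates sensitivity by roughly 3 to 9 points and specificity by about 0.5 to 2. The plan should be changed, but the main validation result is not in doubt.

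**What to change.** Add three statements to section 7.4.

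1. The results for the previously defined cut-offs remain the validation result, whatever refinement follows.
2. If performance of an optimised or refined algorithm is reported, it is internally validated. Every algorithmic selection step (cut-offs, model terms, AIC choice of transformation) is repeated in each bootstrap replicate, and each replicate's rule is applied to the original cohort. The mean optimism is subtracted from sensitivity, specificity and accuracy, and from AUC if the score is refitted. Likelihood ratios are derived from the corrected values. Intervals must reflect the selection; the method can be left to the trial statistician. Any time-window restriction chosen by judgement is reported as exploratory.
3. That algorithm is labelled as derived in TIME and not validated by it.

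The cost is some added text, programming and computing. The sample size does not change. The secondary figures become slightly less favourable, and some optimism remains after correction.
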